This is a phase II randomized placebo-controlled interventional study. Patients will be randomized in a 2:1 allocation of experimental group A to standard of care group B. Experimental group will receive high dose influenza vaccine with a booster high dose flu vaccine one month later. Standard of care arm will receive a single influenza vaccine (standard dose if age <65 and high dose if age \geq 65) and a placebo booster vaccine after one month. Both group A and B will be stratified by disease type to allow for a balanced study population. Patients can be viewed as two distinct populations, those with disease requiring therapy (defined as any plasma cell disorder having at any time required therapy) and those with early disease (defined as asymptomatic multiple myeloma, asymptomatic Waldenstrom macroglobulinemia, or monoclonal gammopathy of undetermined significance). As such, we will stratify patients by disease requiring therapy versus early disease by separately randomizing patients into the two protocol groups but with the same allocation ratio of 2:1. Patients treatment is summarized as follows:

Group (Each group stratified by disease requiring therapy and early disease)	Randomization	Initial Influenza Vaccine at day 0	Second High Dose Influenza Vaccine at day 30 (+14 days/-7days)
Experimental (A)	2	Fluzone® High-Dose	Fluzone® High-Dose
Standard of Care (B)	1	Fluzone® High-Dose if age \geq 65, Standard dose influenza vaccine if age < 65.	Placebo

A Comprehensive Cancer Center Designated
by the National Cancer Institute

Phase: II

YCC Version 4.0 Date: 31-May-2017

pg. 9

STUDY DURATION: 2015-2016 influenza season	TOTAL SAMPLE SIZE: 150 Subjects (100 in experimental group A and 50 in standard of care group B)
DOSING REGIMEN: Fluzone® High-Dose trivalent inactivated influenza vaccine given on day 0 and again on month +1 (+14 days/-7 days) in the experimental group.	

Schedule of Study Assessments

Procedure	2015 – 2016 Flu Season (August to May)				

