To the authors' knowledge, there have not been any prior influenza vaccine studies in patients with monoclonal gammopathies, which have looked at clinical endpoints other than our pilot SHIVERING trial. Clinical endpoints which we plan to assess include number of influenza infections, influenza-related hospitalizations / deaths, and efficacy related to prior therapy. While prior studies have measured serologic response to influenza vaccines in patients with monoclonal gammopathies, there have not been any trials correlating T cell responses. We plan to try to better understand cell mediated immunologic response by looking at T cell functional assays.

Our **hypothesis** is that the administration of Fluzone® High-Dose with booster to all patients with monoclonal gammopathies (irrespective of age) will lead to seroconversion rates exceeding 50% and more importantly, will reduce influenza-related morbidity, prevent interruptions in cancer therapy and reduce disease progression at the end of the influenza season.

In this study, we will administer Fluzone® High-Dose vaccine with a planned booster to patients with monoclonal gammopathies (randomized into the experimental group versus standard of care). The experimental group will receive Fluzone® High-Dose vaccine with a second booster dose after 30 days, regardless of age. In the standard of care group, patients will receive influenza vaccine based on current standard of care clinical practice. Standard of care depends on age; patients ≥ 65 receive a single high dose influenza vaccine, patients < 65 receive a single

A Comprehensive Cancer Center Designated
by the National Cancer Institute

Phase: II

YCC Version 4.0 Date: 31-May-2017

pg. 14

standard dose vaccine. In addition, patients in the standard of care group will receive a placebo vaccine after 30 days, which will aid in the blinding between groups and allow for stricter comparison between groups.

Primary endpoint is a composite of documented influenza infection rate and disease progression (as defined by International Myeloma Working Group criteria) at the end of the flu season. We will also analyze several secondary endpoints including rates of influenza related morbidity, analysis of humoral and cellular immune response to these vaccines, and rate of disease control (defined as lack of disease progression by standard international myeloma working group criteria).

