Approximately 150 of subjects with monoclonal gammopathies will be screened for enrollment and must meet the eligibility criteria below. 100 patients will be randomized into the experimental group and 50 subjects will be randomized into the standard of care group. During screening, patients will be identified by disease type as having either disease requiring therapy or early disease. In order to maintain balanced stratification, patients of each disease type will be separately allocated in the same ratio of 2:1 experimental to control group. If a patient dies or discontinues their participation for any reason, we will not add another patient in their place.

Inclusion Criteria

Subjects must meet the following inclusion/exclusion criteria to be eligible for the study.

Inclusion criteria

1. Understand and voluntarily sign an informed consent form.
2. Age \geq 18 years at the time of signing the informed consent form.
3. Diagnosis of any monoclonal gammopathy: Monoclonal Gammopathy of Undetermined Significance (MGUS), asymptomatic / active multiple myeloma, asymptomatic / active Waldenström Macroglobulinemia (WM).

Exclusion criteria

1. Any serious egg allergy or prior serious adverse reaction to an influenza vaccine.

A Comprehensive Cancer Center Designated
by the National Cancer Institute

Phase: II

YCC Version 4.0 Date: 31-May-2017

pg. 17

2. Use of any other influenza vaccine for the 2015 to 2016 flu season.
3. Women who are pregnant or plan to become pregnant in the study period.

Visit schedule and assessments

Screening Assessments and all on study scheduled visits and assessments are outlined in Section 2 Table of Study Assessments.

At the end of the 2015-2016 flu season between May 1 to May 15, subjects will undergo off study evaluations per the Schedule of Assessments.

Vaccine Administration

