5.4.2 Dosing regimen

The planned vaccine administration for investigation for experimental group is:

- 1) Fluzone® high-dose vaccine after flu vaccines are available (starting August 2015);
- 2) Fluzone® high-dose vaccine as a second booster dose to all subjects in each cohort.

The planned vaccine administration for investigation for standard of care group is:

- 1) Fluzone® high-dose vaccine if age ≥ 65 or standard dose trivalent inactivated influenza vaccine if age <65. Vaccines will be administered based on standard of care practice after flu vaccines are available (starting August 2015);
- 2) Placebo normal saline injection as a second booster dose to all patients in this group.

A Comprehensive Cancer Center Designated
by the National Cancer Institute

Phase: II

YCC Version 4.0 Date: 31-May-2017

pg. 18

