We plan to enroll 50 patients in the standard care group and 100 in the vaccine group for a total of 150. Patients will be separately allocated in this 1:2 ratio based on their disease type of early disease versus active disease in order to maintain balanced stratification between the groups. For each disease type, this 1:2 ratio will be performed in blocks of three in order to maintain balance in the study at all times. A randomization schedule will be prepared by the study biostatistician, [name], in advance of the trial beginning. If the standard care group has 0.70 probability of success (defined above) and the vaccinated group has probability of success equal to 0.90 then the power of this design is 0.93. As another example, if the standard care group has 0.75 probability of success and the vaccinated group has 0.90 probability of success then the power of

A Comprehensive Cancer Center Designated
by the National Cancer Institute

Phase: II

YCC Version 4.0 Date: 31-May-2017

pg. 21

our design is 0.78 at significance level 0.1. Patient deaths which are not related to influenza or disease progression will be censored for efficacy analysis.

Yale University's online OnCore system will be used to randomize the patients. Randomization will be performed by the clinical trials office of Yale University and the information released only to the research pharmacist.

We will monitor the study for the toxicity of the vaccine. The unacceptable toxicities include any serious adverse event grade 3 or higher which is believed to be related to the study vaccine. The tolerability will initially be tested in the first 20 patients in the vaccine arm. We will consider the vaccine tolerable if the rate of vaccine related toxicity is 10% or less and intolerable if 30% or more. If, in the first 20 patients, we observe 5 or more patients with vaccine related toxicity, then the cohort will be terminated early. With this design, the probability of terminating the cohort early is 0.04 if the true but unknown toxicity rate is 10% and 0.76 if the true rate is 30%.

Regulatory Considerations

Institutional Review Board/Ethics Committee approval

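### The disease-type strata are not carried into the analysis, and no effect by age group is planned although age 65 decides the control vaccine

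*Combined protocol and SAP*

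**What the plan says.** **Strata.** Screening and Eligibility says that "patients of each disease type will be separately allocated in the same ratio of 2:1 experimental to control group". Biostatistical Considerations repeats this ("Patients will be separately allocated in this 1:2 ratio based on their disease type of early disease versus active disease") and adds blocks of three. Disease type then disappears: the section defines a yes/no failure (progression or documented influenza), gives one success rate per arm, and names neither a test nor a stratum term.

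**Age.** In the Synopsis, under Study Design, "Standard of care arm will receive a single influenza vaccine", and its type is set by age. The Rationale section says "Standard of care depends on age". Section 5.4.2 gives controls the high-dose vaccine from age 65 and "standard dose trivalent inactivated influenza vaccine if age <65". Every experimental patient gets the high-dose vaccine twice. Age is not a randomisation stratum. The only breakdown of efficacy mentioned anywhere is by prior therapy, in the Rationale section.

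**Power.** With 50 control and 100 vaccine patients, the plan states power 0.93 for success of 0.70 against 0.90. For 0.75 against 0.90 it says "our design is 0.78 at significance level 0.1". It does not say whether that level is one- or two-sided.

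**The concern.** The age rule creates two different comparisons inside one trial:

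| Age | Experimental arm | Control arm | What the contrast tests |
|---|---|---|---|
| Under 65 | high dose, then high dose | standard dose, then placebo | dose plus booster |
| 65 and over | high dose, then high dose | high dose, then placebo | booster alone |

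The pooled estimate is a mixture of the two, weighted by an age mix that the documents do not give. The plan means its estimates to guide larger trials and possibly practice. If only the pooled figure is reported, a success driven by patients under 65 could be taken as evidence for the booster in older patients.

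The strata are a smaller matter. Randomising within disease type and then ignoring it gives away a little precision, and can make the test slightly conservative. The natural analysis is the one that matches the randomisation.

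**Working it through.** **1. The plan's power figures.** Inputs from Biostatistical Considerations: n0 = 50, n1 = 100, success 0.70 or 0.75 against 0.90, level 0.1. For the pooled two-proportion test,

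power = Φ{[(p1 − p0) − z·S0] / S1}, with S0 = √[p̄(1 − p̄)(1/n0 + 1/n1)] and S1 = √[p0(1 − p0)/n0 + p1(1 − p1)/n1].

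Two-sided 0.10 means z = 1.645.

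| Arms | Rates | p̄ | S0 | S1 | Φ of | Power | Printed |
|---|---|---|---|---|---|---|---|
| 50:100 | 0.70 v 0.90 | 0.833 | 0.0645 | 0.0714 | 1.314 | 0.906 | 0.93 |
| 50:100 | 0.75 v 0.90 | 0.850 | 0.0618 | 0.0682 | 0.708 | 0.760 | 0.78 |
| 75:75 | 0.70 v 0.90 | 0.800 | 0.0653 | 0.0632 | 1.464 | 0.9283 | 0.93 |
| 75:75 | 0.75 v 0.90 | 0.825 | 0.0620 | 0.0608 | 0.788 | 0.7847 | 0.78 |

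Exact binomial enumeration of the two-sided test at 50:100 gives 0.914 and 0.766. Equal arms of 75 return both printed figures; the trial's own ratio gives about 0.91 and 0.76-0.77. A one-sided 0.10 test at 50:100 gives 0.950 and 0.850, or 0.924 and 0.793 with continuity correction. The last pair is also within 2 points of the printed figures.

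**2. Value of stratifying by disease type.** The split is an assumption. The Rationale section expects more than two thirds relapsed or refractory patients, so I take 33 treated and 17 early controls, or 42 and 8, with twice as many on vaccine. Overall success is held at the plan's rates.

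- *Realistic case:* early patients fail from influenza only, 20% on control (the protocol's expected rate) and 4% on vaccine (its pilot rate). For 33/17 at 0.70 v 0.90, treated control success is (0.70 − 0.34 × 0.80)/0.66 = 0.648, and treated vaccine success is (0.90 − 0.34 × 0.96)/0.66 = 0.869.
- *Extreme case:* no failures among early patients.

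The table gives two-sided 0.10 power from 1,000,000 simulated trials per scenario, unstratified test then Cochran-Mantel-Haenszel (CMH) without correction:

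| Case | Split | 0.70 v 0.90 | 0.75 v 0.90 |
|---|---|---|---|
| Realistic | 33/17 | 0.917, 0.919 | 0.767, 0.769 |
| Realistic | 42/8 | 0.915, 0.916 | 0.767, 0.768 |
| Extreme | 33/17 | 0.932, 0.945 | 0.784, 0.812 |
| Extreme | 42/8 | 0.921, 0.925 | 0.773, 0.778 |

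The gain is about 0.2 points or less in the realistic case and at most about 3 in the extreme. With no treatment effect and success of 0.6 (treated) and 0.9 (early), 33/17, the unstratified two-sided test rejects in about 8.7% of trials and CMH in 10.2% (40,000 runs), against a nominal 10%.

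**3. What a pooled result can hide (illustration).** Let s be the share aged 65 or over, assumed 30%, 50% or 70%. Take 0.70 v 0.90 under 65, and the same success q in both arms at 65 and over. Arm success is s·q + (1 − s)·0.70 for control and s·q + (1 − s)·0.90 for vaccine, so the true pooled difference is (1 − s) × 20 = 14, 10 or 6 points. For s = 0.5 and q = 0.90 the arms are 0.80 and 0.90. Exact probability that the pooled two-sided 0.10 test is significant:

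| q at 65 and over | s = 30% | s = 50% | s = 70% |
|---|---|---|---|
| 0.90 | 72% | 52% | 29% |
| 0.80 | 67% | 44% | 23% |
| 0.70 | 63% | 40% | 21% |

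**4. Precision by age group.** The 95% half-width is 1.96·√[p0(1 − p0)/n0 + p1(1 − p1)/n1] with p1 = 0.90:

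| Control v vaccine patients | p0 = 0.90 | p0 = 0.80 | p0 = 0.70 |
|---|---|---|---|
| 35 v 70 | 0.122 | 0.150 | 0.167 |
| 25 v 50 | 0.144 | 0.177 | 0.198 |
| 15 v 30 | 0.186 | 0.229 | 0.256 |

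**The case against.** The strongest reply is that the trial asks about a strategy. The hypothesis covers patients of any age, and the comparator is age-dependent standard care, so the pooled contrast is exactly the question posed. That stands, and it is why the pooled comparison should stay primary. It does not remove the need to show the two components, because the difference between them is built into the design and was not found by searching the data.

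Second, intervals of 12 to 26 points around a planned 20-point effect will often fail to separate no booster effect from the full one. That also stands, and it limits the age analysis to estimation. A wide interval at 65 and over still tells the reader how little the trial shows there.

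Third, the age shares and the zero booster effect are my assumptions. The protocol's own evidence leaves the booster's effect open. One earlier study of 70 patients, only 14 of them with myeloma or Waldenström disease, found no serologic gain. Another, in 25 myeloma patients, saw protection rise from 14% to 33%. The pilot (2 of 51 infected) had no control arm. None of these isolates a second high dose, so they do not show that it fails in older patients.

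Fourth, the stratification gain is small. Agreed. Fifth, Version 4.0 is dated 31 May 2017, a year after the final visits of May 2016, so any addition may come too late to count as pre-specified. That affects how the analyses are labelled, not whether they are useful.

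**Conclusion.** The point holds as a worthwhile change to the analysis, not as a flaw that undermines the trial. The age gap matters more: the plan would report one effect for two contrasts. Under the assumptions shown, a significant pooled result with no booster effect at 65 and over occurs in 21% to 72% of trials. That range illustrates the risk; it is not a prediction. The disease-type gap is small.

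A reader might infer more than the documents support:

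- *That the unstated sidedness raises the false-positive risk above what was declared.* With success 0.70 in both arms, a false claim of benefit has exact probability 0.053 (two-sided 0.10), 0.072 (one-sided, corrected) or 0.101 (one-sided, uncorrected). All are at or about 0.1 or below. With 35 of 50 control successes, the smallest positive vaccine result moves only from 82 to 81 or 80 of 100. This is missing detail.
- *That ignoring the strata invalidates the test.* It does not; the test is at worst slightly conservative.
- *That the match at 75:75 proves the 2:1 ratio was overlooked and a two-sided test intended.* It suggests both and proves neither, since a one-sided corrected test at 50:100 also comes close. The shortfall is about 1 to 2 points of power.
- *That the pooled comparison is biased.* It is not; its meaning depends on the age mix.

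**What to change.** In Biostatistical Considerations:

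1. Make the primary analysis a Cochran-Mantel-Haenszel test stratified by disease type as randomised, with a stratified risk difference and confidence interval.
2. Add, as a secondary and estimation-only analysis, the risk difference with confidence interval within patients under 65 and within those 65 and over. State what each contrast tests and how imprecise it is (about ±12 to 26 points), and make no significance claim. Label it post hoc if the data are already unblinded.
3. As a minor correction, say whether the 0.1 level is one- or two-sided and restate the power for 50:100. If it is two-sided, that is about 0.91 and 0.76-0.77.

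The cost is wording and a few lines of analysis. Disease type and age are both known at enrolment. No extra patients or procedures are needed, and nothing here asks for a change to the vaccines, the randomisation or the sample size.

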In this study, we will administer Fluzone® High-Dose vaccine with a planned booster to patients with monoclonal gammopathies irrespective of age versus a standard of care control group. Primary endpoint is composite of documented influenza infection rate and disease progression (as defined by International Myeloma Working Group criteria) at the end of the flu season. Based on the background data, we expect a higher rate of success in the experimental arm. As such, we power for success rates of 90% and 70% in the experimental and control arms, respectively. We will also analyze several secondary endpoints including rates of influenza related morbidity, the analysis of humoral and cellular immune response to these vaccines and the rate of disease control (defined as lack of disease progression by standard international myeloma working group criteria).

By comparing this experimental approach directly to standard of care, data from estimates of effectiveness will inform the design of larger future controlled studies. As such, the data from this study can lead to practice-changing results. The data on immune correlates will also yield important information about *in vivo* "immune-competence" of these individuals, which in turn is important to design trials with emerging immune therapies.

STUDY Endpoints:

Primary:

- 1) The primary clinical endpoint of this study is: to measure a composite of documented influenza infection rate and disease progression (as defined by International Myeloma Working Group criteria) at the end of the flu season following a high dose influenza vaccine booster strategy versus standard of care.

A Comprehensive Cancer Center Designated
by the National Cancer Institute

Phase: II

YCC Version 4.0 Date: 31-May-2017

pg. 8

Secondary:

1. evaluate rates of serologic protection (defined as HAI titer >40) following Fluzone® High-Dose influenza vaccine with booster dosing versus standard of care.
2. measure T cell subsets and flu-specific T cell responses following high dose influenza vaccine booster dosing strategy versus standard of care.

STUDY DESIGN:

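### Do the stated powers of 0.93 and 0.78 belong to an equal 75:75 split rather than to the planned 50:100 allocation?

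*Combined protocol and SAP*

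**What the plan says.** The sample size is set in the Biostatistical Considerations section: "We plan to enroll 50 patients in the standard care group and 100 in the vaccine group for a total of 150". The power statement follows in the same paragraph. Its first example begins "If the standard care group has 0.70 probability of success (defined above") and ends by saying that if the "vaccinated group has probability of success equal to 0.90 then the power of this design is 0.93". The second supposes that "if the standard care group has 0.75 probability of success and the vaccinated group has 0.90 probability of success" and concludes that the power of "our design is 0.78 at significance level 0.1".

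The Protocol Synopsis repeats the main scenario: "we power for success rates of 90% and 70% in the experimental and control arms, respectively". The 2:1 allocation, or 100 and 50 patients, is also given in the Study Design part of the synopsis, under Screening and Eligibility, and in section 5.4.1. Nowhere is an equal split mentioned. The plan does not name the primary test, its sidedness or the power formula.

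**The concern.** For a fixed total, unequal allocation usually costs some power. A reader who checks the two figures with the textbook two-proportion formula at a two-sided 0.10 level finds that 50:100 falls short of both, while 75:75 matches both to two decimals. Several other methods at 50:100 also miss the pair. One-sided Fisher gives 0.933 and 0.801, two-sided Fisher 0.896 and 0.736, and the one-sided pooled z test 0.950 and 0.850. The natural suspicion is that the calculation was done for equal arms and carried over to a 2:1 design.

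These two figures are the only quantitative support for the sample size. If they belonged to another design, the type II error in the main scenario would be 9.4% on that formula rather than 7%. Because the level is printed only with the second figure and no sidedness is given, the error rate behind 0.93 also seemed open.

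**Working it through.** **Inputs** (Biostatistical Considerations): n₁ = 50 standard care, n₂ = 100 vaccine; success rates 0.70 against 0.90 and 0.75 against 0.90; level 0.1. Assumed, because the plan does not say: a Pearson chi-square test with 1 degree of freedom, critical value 2.706 = 1.645².

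**Step 1. The plan's figures at 50:100.** The usual power calculation for the Pearson test takes the statistic as noncentral chi-square with

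λ = (p₂ − p₁)² / [p̄(1 − p̄)(1/n₁ + 1/n₂)], where p̄ = (n₁p₁ + n₂p₂)/(n₁ + n₂).

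With 1 degree of freedom, power is Φ(√λ − 1.645) apart from a negligible second tail.

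- 0.70 against 0.90: p̄ = (35 + 90)/150 = 0.8333; null variance = 0.13889 × 0.03 = 0.0041667; λ = 0.04/0.0041667 = 9.60; √λ = 3.098; power = Φ(1.4535) = 0.9270, which rounds to **0.93**.
- 0.75 against 0.90: p̄ = (37.5 + 90)/150 = 0.85; null variance = 0.1275 × 0.03 = 0.003825; λ = 0.0225/0.003825 = 5.88; √λ = 2.425; power = Φ(0.7805) = 0.7825, which rounds to **0.78**.

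Both printed figures are reproduced at the planned allocation.

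**Step 2. The same formula at 75:75.**

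- First example: p̄ = 0.80; λ = 0.04/(0.16 × 2/75) = 9.375; power = Φ(3.062 − 1.645) = 0.922.
- Second example: p̄ = 0.825; λ = 0.0225/(0.144375 × 2/75) = 5.844; power = Φ(2.417 − 1.645) = 0.780.

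Here the equal split would have printed 0.92, not 0.93.

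**Step 3. Why the textbook formula differs.** It uses the null standard deviation for the critical value but the alternative one for the spread of the estimate:

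power = Φ{[(p₂ − p₁) − 1.645·s₀]/s₁}, with s₁² = p₁(1 − p₁)/n₁ + p₂(1 − p₂)/n₂.

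- 50:100, first example: s₀ = 0.06455, s₁ = √(0.0042 + 0.0009) = 0.07141; power = Φ(1.314) = 0.9055.
- 50:100, second example: s₀ = 0.06185, s₁ = 0.06819; power = Φ(0.708) = 0.7605.
- 75:75: 0.9283 and 0.7847.

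The smaller arm has the larger binomial variance, so s₁ exceeds s₀ at 50:100. The noncentral chi-square formula in effect uses s₀ in both places. The gaps of 0.9270 − 0.9055 = 0.0215 and 0.7825 − 0.7605 = 0.0220 come from that choice alone.

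**Step 4. The level behind 0.93.** With the Step 1 formula, replacing 1.645 by 1.960 (two-sided 0.05) gives Φ(1.138) = 0.87 and Φ(0.465) = 0.68. Replacing it by 1.282 (one-sided 0.10) gives Φ(1.817) = 0.97 and Φ(1.144) = 0.87. Of these three, only two-sided 0.10 gives the printed pair, and it gives both members.

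**Step 5. Spread of accepted methods at 50:100, level 0.10.**

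| Method | 0.70 v 0.90 | 0.75 v 0.90 |
|---|---|---|
| Plan | 0.93 | 0.78 |
| Noncentral chi-square | 0.927 | 0.782 |
| Two-sided normal approximation, s₀ and s₁ | 0.906 | 0.760 |
| Two-sided chi-square, exact enumeration | 0.914 | 0.766 |
| One-sided normal approximation, continuity-corrected | 0.924 | 0.793 |

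The last three differ from the plan by at most 2.5 points, and for the second example they fall on both sides of 0.78.

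**The case for a change.** The strongest case for the concern has three parts.

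First, the 75:75 match under a textbook formula is real, and many methods at 50:100 miss the pair. But that formula is not the only standard one. Once the noncentral chi-square calculation is included, a 50:100 method fits both figures equally well. A match at 75:75 is then no evidence that the allocation was ignored, above all in a paragraph that states 50 and 100 just before calling these the powers of its design.

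Second, exact enumeration of the two-sided chi-square test at 50:100 gives 0.914 and 0.766, so the printed figures are somewhat optimistic: 0.93 − 0.914 = 0.016 and 0.78 − 0.766 = 0.014. This stands, but it is ordinary approximation error. The formula behind the proposed 0.91 and 0.76 is itself an approximation, lying below the exact values by 0.914 − 0.906 = 0.008 and 0.766 − 0.760 = 0.006.

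Third, neither test nor sidedness is named, and "at significance level 0.1" is printed once. In principle that leaves open whether the error rate in the direction of benefit is 5% or 10%. As a remark about completeness this also stands. The two examples are consecutive and concern one design, so the level is naturally read as covering both, and Step 4 supports that reading. It does not make either power figure wrong.

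**Conclusion.** The concern does not hold. A standard power calculation at the planned 50:100 allocation and level 0.10 gives 0.927 and 0.782, which round to the plan's 0.93 and 0.78; no equal split is needed to explain them. Other accepted methods at the same allocation and level differ by about 2.5 points or less. In the main scenario the two-sided results stay between 0.906 and 0.927, so the adequacy of 150 patients is not in question.

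This rests on two assumptions: that the level of 0.1 applies to both examples, and that a Pearson chi-square calculation is a fair reading of an unnamed test. The plan does not confirm the second, so the method is inferred; what is shown is that the figures are consistent with the stated design. All calculations count the full 150 patients as evaluable, so losses to follow-up, which are not replaced, are a separate matter. What remains is the unnamed test and sidedness, a gap in detail. Replacing the figures with 0.91 and 0.76 would exchange one accepted approximation for another and change no conclusion.
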